5.4.1.2 Nivolumab Dosing

Nivolumab administration should start at least 30 minutes after the end of the NKTR-214 administration. Nivolumab will be administered IV over 30 (\pm 5) minutes at a dose of 360 mg. The duration of infusion of nivolumab may be increased if necessary (e.g., patient history of infusion reaction) (see Pharmacy Manual for details).

There will be no dose escalations or reductions of nivolumab allowed. Patients may be dosed no less than 18 days from the previous dose. Premedications are not recommended for the first dose of nivolumab.

Patients should be carefully monitored for infusion reactions during nivolumab administration. If an acute infusion reaction is noted, patients should be managed according to Section 5.13.9.

[REDACTED]

[REDACTED]

[REDACTED]

Instructions for dilution and infusion of nivolumab injection will be provided in the Pharmacy Manual.

5.4.1.3 Sunitinib and Cabozantinib Dosing

Sunitinib will be administered on a 6-week cycle, starting at a dose of 50 mg once daily for 4 weeks, followed by 2 weeks of no treatment. Cabozantinib will be administered at a starting dose of 60 mg once daily; for patients with moderate hepatic impairment (Child Pugh Class B) the starting dose of cabozantinib will be 40 mg once daily. Food fasting is recommended for 2 hours before and 1 hour after cabozantinib administration. [Table 7](#) provides the permitted doses for sunitinib and cabozantinib. Refer to the sunitinib ([Sutent[®]](#)) and cabozantinib ([Cabometyx[®]](#)) US Prescribing Information and/or the corresponding SmPC for updated dosing guidance or further information.

5.4.2 Monitoring Vital Signs and Hydration Guidelines

The study site must be equipped for medical emergencies.

5.4.2.1 Frequent Vital Signs

Refer to Section [8.17](#) for vital sign measurements, which are to be monitored according to the Schedule of Events (Section [1.2](#)).

5.4.2.2 Hydration Guidelines for Arm A

Important safety information and hydration instructions are to be provided to patients randomized to Arm A. Details regarding intravenous and oral hydration will be captured in the

electronic data capture (EDC). Oral hydration details during Cycle 1 will be captured in a patient hydration diary.

Adequate hydration mitigates the development of hypotension associated with NKTR-214 administration. Hydration and renal function must be assessed within 24 hours, or as soon as locally feasible, prior to NKTR-214 study drug administration see [Appendix 3](#) for the list of analytes that require collection and evaluation prior to NKTR-214 study drug administration). For patients who must delay study treatment due to creatinine increase, see additional information regarding criteria to delay (Sections [5.13.1](#) and [5.13.2](#)), resume (Section [5.13.7](#)), or permanently discontinue study treatment (Section [5.14](#)). Underlying reasons for decreased oral intake (e.g., nausea) should be addressed and treatment (e.g., IV hydration) should be provided. The Investigator may modify these recommendations based on the needs of the individual patient. Patients will also be provided a handout with hydration guidance.

Patients randomized to Arm A should be administered 1 liter of IV fluid on the day of each dosing of NKTR-214. Patients are to be instructed that for the next 3 days after administration of NKTR-214, they should drink at least 2 liters per day of self-administered oral hydration. Avoid activity that may contribute to dehydration (including, but not limited to, strenuous activity, long hot showers, and saunas) on the day of NKTR-214 administration and for the next 3 days after NKTR-214 administration.

Per clinical judgment, IV fluids may be administered at any time during any cycle. The Investigator may decide to forego administering IV fluids to a patient or adjust the recommendation for self-oral hydration to a particular patient if this is deemed in the best interest of the patient (e.g., evidence of fluid overload). Advise patients with orthostatic symptoms to call their treating oncologist and consider increasing oral hydration.

Patients with pre-existing adrenal impairment requiring corticosteroid supplementation may be at increased risk for hypotensive episodes during treatment with NKTR-214 (See Section [5.13.5](#)).

Between 2 and 4 days, inclusive, following administration of the first 2 doses of NKTR-214, site personnel must contact the patient (by telephone or clinic visit) to remind the patient of the oral hydration guidelines, to assess for any symptomatology and compliance with the guidelines, and document compliance and symptoms from the discussion (Section [1.2](#)). Following subsequent NKTR-214 administrations, the oral hydration follow-up should be conducted as clinically indicated for patients receiving NKTR-214.

5.4.3 Duration of Treatment

Patients will remain on treatment until:

- Disease progression in the absence of clinical benefit as determined by the Investigator
- Death
- Unacceptable toxicity

- Symptomatic deterioration
- 2 years from Cycle 1 Day 1 (Arm A only)
- Investigator's decision to discontinue treatment
- Patient decision to discontinue treatment
- Patient withdraws consent
- Patient is lost to follow-up
- The Sponsor decides to terminate the study

5.4.4 Treatment Beyond Progression

Accumulating evidence indicates that a minority of patients with solid tumors treated with immunotherapy may derive clinical benefit despite initial evidence of PD ([Wolchock, 2009](#); [Nishino, 2015](#)). Study treatment decisions will be based on the Investigator's assessment of tumor images and not on the BICR assessment (Section 7.4). Patients in both treatment arms will be permitted to continue on treatment beyond initial mRECIST 1.1-defined PD as long as they meet the following criteria:

- Investigator-assessed clinical benefit
- Patient tolerates study drug(s)
- Patient has stable performance status
- Treatment beyond progression will not delay an imminent intervention to prevent serious complications of disease progression (e.g., central nervous system metastases requiring immediate treatment).
- Patient provides written informed consent prior to receiving additional study treatment. All other elements of the main consent including description of reasonably foreseeable risks or discomforts, or other alternative treatment options will still apply.

The assessment of clinical benefit should take into account whether the patient is clinically deteriorating and unlikely to receive further benefit from continued treatment. All decisions to continue treatment beyond initial progression, including an assessment of the risk/benefit of continuing with study drug(s), must be documented in the study records. The ICF contains language explaining treatment beyond progression; should the Investigator recommend continuing treatment following disease progression, the patient must be re-consented prior to continuing study treatment.

For patients who stay on treatment beyond mRECIST 1.1-defined PD, all study procedures (Section 1.2) should be performed continuously, including radiographic assessment by CT (preferred) or MRI on the described schedule in Section 7.0. CT/MRI assessments should continue until criteria for treatment discontinuation are met and BICR-assessed progression has

occurred. Tumor assessments are no longer required if subsequent anticancer therapy is started, even if the patient has not yet progressed.

Treatment beyond progression should be stopped when Investigator assesses a loss of clinical benefit. The criteria may include clinical disease progression, second PD of target lesions per mRECIST 1.1, radiographic progression of non-target lesions, or new lesions. Discussion with the Medical Monitor is encouraged.

5.5 Discontinuation from Study Treatment

Patients may choose to discontinue the trial at any time, for any reason, and without prejudice to further treatment. Patients may discontinue treatment of all or one of the study drugs based on AEs (see Section 5.13).

Reasons for discontinuation of study treatment are listed in Section 5.14.

In the event of a patient's withdrawal, the Investigator will promptly notify the Sponsor and make every effort to complete the Long-Term Follow-Up Schedule of Events specified in Table 4 (Section 1.2).

A patient may also be withdrawn from investigational product/study by the Sponsor, Regulatory Authorities, or Institutional Review Boards (IRBs)/Independent Ethics Committees (IECs).

5.6 Long-Term Follow-Up

Long-term follow-up comprises 2 Safety Follow-Up Visits and Survival Follow-Up. For patients who discontinue study treatment, radiographic tumor assessments will continue to be collected every 9 weeks (± 7 days) from randomization through (and inclusive of) Week 54 and then every 12 weeks (± 7 days) until both BICR and Investigator's assessments of tumor images have determined progression, patient withdraws consent, patient begins a subsequent anticancer therapy, loss to follow up, death, or study termination by the Sponsor. Additional assessments are described in Table 4.

5.6.1 Safety Follow Up

- Safety Follow-up Visit 1 should occur 30 (± 7) days from the last dose of all study drug, or at the time of permanent treatment discontinuation if discontinuation is after the Safety Follow Up Visit 1 window.
- Safety Follow-up Visit 2 occurs 100 (± 7) days from the last dose of all study drug. Safety follow-up visits should occur regardless of initiation of subsequent anticancer therapy.
- Both Safety Follow-Up Visits should be conducted in person.
- Per clinical judgment, the patient may come in earlier for additional follow up.

- Patients will also be followed for safety until resolution or permanent sequelae of all toxicities attributable to study drugs (NKTR-214 and/or nivolumab or TKI) as outlined in Sections 8.5 and 8.8.
- For AE and SAE reporting periods, please refer to Sections 8.5 and 8.7.

5.6.2 Survival Follow Up

- All patients will be contacted for survival every 12 weeks (\pm 14 days) following the Safety Follow-Up Visit 2 (or following last contact with the patient if Safety Follow-Up Visit 2 is missed).
- Survival visits may be conducted in person or by telephone.
- Information about subsequent anticancer therapy will also be collected during these contacts.
- The Sponsor may request that survival data be collected on all treated patients outside of the scheduled contacts. At the time of this request, each patient will be contacted to determine their survival status unless the patient has withdrawn consent for all contact or is lost to follow-up. Patients are not considered lost to follow up until after demonstration of due diligence with follow-up efforts. Alternative methods to determine survival status may be used (e.g., access to medical records and public record searches) as allowed by local regulations and/or guidelines.
- For patients who discontinue study treatment, radiographic tumor assessments will continue to be collected every 9 weeks (\pm 7 days) from randomization through (and inclusive of) Week 54 and then every 12 weeks (\pm 7 days) until both BICR and Investigator's assessments of tumor images have determined progression, patient withdraws consent, death, initiation of subsequent anticancer therapy, loss to follow up, or study termination by the Sponsor.
- Additional subsequent anticancer therapy details such as regimen, setting of the regimen, line of therapy, start date and end date of each regimen, best response to the regimen, and date of progression after next line of therapy will be collected.
- Survival follow up should continue until patient withdrawal of consent for survival follow up, death, loss to follow-up, or study termination by the Sponsor.

5.7 End of Study

End of study is defined as no more than 3 years after the last patient received their first dose of NKTR-214 or Sponsor decision to terminate the study, whichever comes first.

5.8 Tumor and Radiographic Assessments

Tumor assessments for all patients will be performed as specified in Section 1.2.

Tumor response will be evaluated using mRECIST 1.1 described in Section 7.0.

Radiographic assessments (chest/abdomen/pelvis) are required for all patients for tumor measurements. MRI of the brain without and with contrast is required for patients at baseline. CT of the brain (without and with contrast) can be performed if MRI is contraindicated.

Documented tumor measurements are required using CT scans, MRI, physical examination, and/or digital photography, as appropriate. Any imaging used to assess disease at any time point will be submitted for an independent radiology review. Clinical information (palliative radiotherapy on-study, surgical excision of any lesion, details of paracentesis and thoracocentesis) must be provided to the BICR team.

The same method of assessment (CT or MRI and/or digital photography) and the same technique for acquisition of images must be used for all study assessments (contrast must be used unless medically contraindicated). Baseline imaging should be done at the same institution/facility that will be used to measure response during the patient's participation in the study. Radiographic assessments and efficacy analyses will be conducted by the Investigator site as well as the independent radiology review.

If a patient has an unconfirmed PR or CR, an early scan is recommended 4 weeks later (e.g., if the initial observation of PR was seen at Week 9, a Week 13 scan should occur); subsequent tumor assessments must remain on the original assessment schedule (i.e., at Week 18, Week 27, Week 36, Week 45, etc.). For patients with unconfirmed progressive disease, subsequent tumor assessments must remain on the original assessment schedule (i.e., at Week 18, Week 27, Week 36, etc.), unless an early scan is clinically indicated.

ORR and PFS will be evaluated by a BICR as part of this clinical study. Images must be submitted to the BICR on the schedule outlined in the Study 17-214-09/CA045002 Imaging Manual. Patients who discontinue study treatment should continue to have tumor assessments until both BICR and Investigator's assessments of tumor images have determined progression or a subsequent anticancer therapy is started (Section 5.6). Patients who continue treatment beyond BICR-confirmed progression (Section 5.4.4) will continue to have tumor assessments until documentation of PD by the Investigator.

5.9 Pharmacokinetic, Biomarker, XXXXXXXXXX

For Arm A, blood samples for PK analyses of NKTR-214, its metabolites, and nivolumab will be collected as described in [Table 6](#).

Table 6: Pharmacokinetic, Biomarker, [REDACTED]

Study Day of Sample Collection (1 Cycle = 6 weeks)	Event	Time (Relative to Start of NKTR-214 Infusion) Hour: Min	NKTR-214 PK Blood Sample ^d	[REDACTED]	Nivolumab PK Blood Sample	[REDACTED]	CVA Biomarkers
Cycle 1 Day 1	Pre-dose	00:00	X	■	X	■	X ^e
	EOI ^a	00:30	X				
		4:00 ^b	X				
Cycle 1 Day 3 ^c		48:00	X				
Cycle 1 Day 5 ^c		96:00	X				
Cycle 1 Day 8 ^c		168:00	X				
Cycle 1 Day 22	Pre-dose	00:00	X	■	X	■	X ^e
Cycle 3 Day 1	Pre-dose	00:00	X	■	X	■	X ^e
	EOI ^a	00:30	X				
Cycle 4 Day 1	Pre-dose	00:00					X ^e
Cycle 6 Day 1	Pre-dose	00:00	X	■	X	■	X ^e
Cycle 9 Day 1	Pre-dose	00:00	X	■	X	■	X ^e
Cycle 12 Day 1	Pre-dose	00:00	X	■	X	■	X ^e
Cycle 15 Day 1	Pre-dose	00:00	X	■	X	■	X ^e
Safety Follow Up 1				■	X	■	
Safety Follow Up 2				■	X	■	
Time of CVA event							X ^e

CVA = cerebrovascular accident; EOI = end of infusion; [REDACTED]; TIA = transient ischemic attack

- a. This sample should be taken immediately prior to the stopping NKTR-214 infusion (preferably within 2 minutes prior to the end of infusion). If the end of infusion is delayed to beyond the nominal infusion duration, the collection of this sample should also be delayed accordingly.
- b. Time window is ±1 hour for this sample (i.e., range 03:00 to 05:00 hours). Sample is preferred as close to 04:00 hours as is clinically feasible.
- c. Time windows: -1 day for C1D3 (24-48 hours relative to start of NKTR-214 infusion), ± 1 day for C1D5 and -1 day for C1D8
- d. [REDACTED]
- e. [REDACTED]

[REDACTED] CVA and TIA biomarker samples will be obtained from patients from whom a Cycle 1 Day 1 biomarker sample has been collected (see Section 5.10.3).

Sites may only opt out of PK [REDACTED] sampling if they meet one of the following criteria: inability to process these samples, insufficient storage facilities, or unavailable courier pickup / dry ice.

5.9.1 Pharmacokinetics

For patients randomized to Arm A, blood samples for PK analysis will be collected and processed as outlined in a Laboratory Manual that will be provided to the site. All on-treatment time points are intended to align with days on which study drug is administered; if dosing occurs on a different day, the PK sampling should be adjusted accordingly. If it is known that a dose is going to be delayed, then the pre-dose sample should be collected just prior to the delayed dose. However, if a pre-dose sample is collected but the dose is subsequently delayed, an additional pre-dose sample should not be collected. All pre-dose samples should be collected within 24 hours before the start of any dose infusion.

For all PK blood samples, the date and actual time collected must be recorded. For patients whose only peripheral access is via a venous access device or peripherally inserted central catheter, refer to the Laboratory Manual for the proper technique to ensure undiluted whole blood for PK assessments.

Serum PK samples will be analyzed for nivolumab by a validated ligand binding assay. Plasma PK samples will be analyzed for NKTR-214-RC (related cytokines; mixture of compounds containing IL-2 independent of PEG conjugation status) and total PEG (mixture of compounds containing PEG independent of conjugation status to IL-2) by validated ligand binding assays as well as NKTR-214-AC (active cytokines; mixture of 2-PEG-IL-2, 1-PEG-IL-2, and free IL-2) by a qualified ligand binding assay.

[REDACTED]

[REDACTED]

[REDACTED]

[REDACTED]

[REDACTED]

[REDACTED]

[REDACTED]

[REDACTED]

[REDACTED]

[REDACTED]

[REDACTED]

[REDACTED]

[REDACTED]

[REDACTED]

[REDACTED]

[REDACTED]

[REDACTED]

Serum samples will be collected and processed as outlined in the Laboratory Manual that will be provided to the site.

5.10 Biomarkers

A variety of factors that could potentially predict clinical responses to NKTR-214 combined with nivolumab or to TKIs will be investigated in peripheral blood and in tumor specimens taken from all patients prior to, and on treatment and as outlined in Table 6 and the Schedule of Events (Table 1 through Table 4), respectively. Data from these investigations will be evaluated for associations with response, survival (OS, PFS), and/or safety (AE) if data allows. [REDACTED]

[REDACTED]

Complete instructions on the collection, processing, handling and shipment of all samples described herein will be provided in the Laboratory Manual.

Sites may only opt out of biomarker sampling if they meet one of the following criteria: inability to process these samples, insufficient storage facilities, or unavailable courier pickup / dry ice.

5.10.1 Tumor Tissue Biopsy Collection

All patients must have tumor tissue identified and available to be sent during the Screening period:

- Most recent archival sample prior to randomization, from a site not previously irradiated and with no intervening treatment between time of acquisition and randomization

OR

- A fresh pre-treatment biopsy obtained during the Screening Period.

Archival tissue should be provided in a formalin-fixed paraffin-embedded (FFPE) block or as unstained slides (minimum of 8 slides, preferably 20 slides) that have been sectioned within the 3 months prior to randomization. If 8 unstained slides are not available, fewer slides may be submitted; please contact the Medical Monitor for written approval. Leftover tissue blocks, but not slides, will be returned upon request.

Tumor samples must be a core biopsy, punch biopsy, excisional biopsy, or surgical specimen. Biopsy in bone lesion cannot be accepted. Fine needle aspirates/biopsy or other cytology specimens are insufficient for randomization. Biopsies of bone lesions that do not have a soft tissue component are also unacceptable for submission. Target lesions should not be biopsied unless there are no other lesions suitable for biopsy.

Collection of tissue samples in Cycle 1 between Days 14 and 21 and at the time of PD is optional but highly encouraged as they may help inform on the underlying biology of early

response/progression, and the biological mechanisms underlying acquired and/or de novo resistance to the drug(s) administered.

Pre-treatment tumor samples will be submitted for central PD-L1 IHC assessment. PD-L1 expression is defined as the percent of tumor cell membrane staining in a minimum of 100 evaluable tumor cells per validated Dako PD-L1 PharmDx 28-8 IHC assay. PD-L1 stained tissue sections will be assessed by a pathologist and scored as PD-L1 expression $\geq 1\%$ or PD-L1 expression $< 1\%$ based on the frequency of tumor cell surface PD-L1 staining. Samples that have < 100 evaluable cells are considered not evaluable. Where membrane staining is obscured by high cytoplasmic staining, but the tumor tissue sample contains the minimum number of evaluable tumor cells, samples will be deemed PD-L1 indeterminate.

[REDACTED]

[REDACTED]

[REDACTED]

[REDACTED]

[REDACTED]

[REDACTED]

[Redacted text block containing multiple paragraphs of obscured content]

5.11 Medical Resource Utilization and Health Economics

Health care resource utilization data will be collected for all randomized patients using an internal case report form (CRF) developed for use in previous trials. The form, which is completed by study staff, records information about hospital admissions, including number of

days spent in various wards and discharge diagnosis, as well as non-protocol specified visits related to study therapy, including date of visit, reason for visit, and type of visit. The health care resource utilization data will be used to support subsequent economic evaluations.

5.12 Health-Related Quality of Life (HRQoL)

Patients will be asked to complete the NCCN/FACT Symptom Index for Kidney Cancer (FKSI-19), EQ-5D-3L, and selected items from the PRO-CTCAE. Refer to Section 7.6 for additional information.

5.13 Dosage Modification

Every effort should be made to follow planned dosing schedules for all study drugs in both treatment arms. Study drug administration may be delayed or modified for toxicity as described below and must be discontinued as required by criteria described in Section 5.14.

Dose modification for NKTR-214 and nivolumab in Arm A may be considered independently based on Investigator assessment of relationship of a toxicity to each of the study drugs. If only one of the study drugs meets the criteria for dose delay, then administration of the other study drug may be continued or delayed at the discretion of the Investigator. Likewise, in the event that one of the study drugs in Arm A is permanently discontinued due to toxicities, the other can continue to be administered.

Patients who require delay of nivolumab or NKTR-214 should be re-evaluated weekly or more frequently if clinically indicated and should resume treatment with combination of NKTR-214 and nivolumab when retreatment criteria are met (Section 5.13.7). Immuno-oncology agents are associated with AEs that can differ in severity and duration from AEs caused by other therapeutic classes. NKTR-214 and nivolumab are considered an immuno-oncology agent in this protocol. Early recognition and management of AEs associated with immuno-oncology agents may mitigate severe toxicity.

For patients randomized to Arm A: NKTR-214 or nivolumab administration defines a scheduled nominal dosing visit (i.e., Cycle X Day 1, Cycle X Day 22). If a patient is assessed for an intended nominal dosing visit but study drug is not administered (e.g., due to an AE requiring dose delay, drug unavailable), any assessments performed during that visit should be recorded as “unscheduled.” When study drug administration resumes, all assessments should be performed as scheduled for the next nominal dosing visit (i.e., Cycle X Day 1 or Cycle X Day 22 Visit).

For patients randomized to Arm B: Cycle 1 Day 1 is defined by the date that the first dose of sunitinib or cabozantinib is administered. Within a cycle, missed doses of sunitinib should be skipped and not replaced. Scheduled Cycle X Day 1 and Cycle X Day 22 visits are fixed relative to Cycle 1 Day 1, regardless of dose delays. If drug dosing is delayed at the time of these scheduled visits (e.g., due to an AE requiring dose delay, drug unavailable), the cycle visit is not shifted and all assessments should be performed as scheduled.

Tumor assessments for all patients should continue as per protocol even if dosing is delayed.

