Administer Study Drug	X				X	X	X	The first dose should be administered within 5 calendar days following randomization. NKTR-214 0.006 mg/kg IV q3w + Nivolumab 360 mg IV q3w Refer to Section 5.4.1 for sequential dosing instructions. If the IV study drug administration is delayed, the procedures scheduled for that visit should be performed with the delayed visit for drug administration (does not apply to tumor assessments; see Body Imaging below).
Administer IV fluids	X				X	X	X	May be withheld if deemed in the best interest of the patient by the Investigator Refer to Section 5.4.2.2 for further details.
Review hydration guidelines with patient	X				X	X	X	Applicable only while NKTR-214 is administered

Abbreviations used in this table appear on the final page of [Table 4](#).

Table 2: On-Treatment Schedule of Events for Arm A (Contd)

Procedure ^a	Arm A NKTR-214 0.006 mg/kg IV q3w and Nivolumab 360 mg IV q3w Cycle = 6 Weeks							Notes
	Cycle 1					Cycle 2 and all subsequent cycles		
	Day 1	Day 3 (-1 day)	Day 5 (± 1 day)	Day 8 (-1 day)	Day 22 (± 3 days)	Day 1 (± 3 days)	Day 22 (± 3 days)	
Oral Hydration Follow-up	X ¹				X ¹	X ²	X ²	X ¹ = Between 2 and 4 days following the first 2 administrations of NKTR-214 in Cycle 1, site personnel must contact the patient (by telephone or clinic visit) to remind the patient of the oral hydration guidelines, to assess for any symptomatology and compliance with the guidelines, and document compliance and symptoms from the discussion. X ² = For subsequent NKTR-214 administrations in Cycle 2 and beyond, oral hydration follow-up should be conducted as clinically indicated between 2 and 4 days following NKTR-214 administration (see Section 5.4.2.2).
Safety Assessment								
Targeted Physical Examination, Weight, Vital Signs	X	VW	VW	VW	VW	X	VW	Vital Signs: blood pressure, heart rate, temperature Vital signs should be monitored at the following timepoints relative to study drug dose administrations: 
 Pre-dose (NKTR-214) Within 30 minutes after administration of nivolumab VW = Vital Signs and Weight only
Karnofsky Performance Status	X					X		See Appendix 2 .

Abbreviations used in this table appear on the final page of [Table 4](#).

Table 2: On-Treatment Schedule of Events for Arm A (Contd)

Procedure ^a	Arm A NKTR-214 0.006 mg/kg IV q3w and Nivolumab 360 mg IV q3w Cycle = 6 Weeks							Notes
	Cycle 1					Cycle 2 and all subsequent cycles		

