3.2 Secondary Objectives

The key secondary objectives are:

- To compare the PFS by BICR using mRECIST 1.1 of NKTR-214 combined with nivolumab to TKI monotherapy (sunitinib or cabozantinib) in IMDC intermediate- or poor-risk patients with previously untreated advanced RCC
- To compare the PFS by BICR using mRECIST 1.1 of NKTR-214 combined with nivolumab to TKI monotherapy (sunitinib or cabozantinib) in IMDC all-risk patients with previously untreated advanced RCC

The other secondary objectives are:

- To estimate the incidence of AEs of NKTR-214 combined with nivolumab versus TKI monotherapy (sunitinib or cabozantinib) in patients with previously untreated advanced RCC
- To evaluate whether PD-L1 expression on tumor cells ($< 1\%$ vs $\geq 1\%$) using the PD-L1 immunohistochemistry (IHC) 28-8 pharmDx assay is a predictive biomarker for ORR, PFS, and OS in patients with previously untreated advanced RCC
- To characterize changes in cancer-related symptoms and quality-of-life in patients with previously untreated advanced RCC using the National Comprehensive Cancer Network/Functional Assessment of Cancer Therapy (NCCN/FACT) Symptom Index for Kidney Cancer (FKSI-19)

[REDACTED]

[REDACTED]

[REDACTED]

[REDACTED]

[REDACTED]

[REDACTED]

[REDACTED]

[REDACTED]

[REDACTED]

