7.6 Health-Related Quality of Life (HRQoL)

Patients will be asked to complete the NCCN/FACT Symptom Index for Kidney Cancer (FKSI-19), 3-level version of the EuroQol Group's EQ-5D (EQ-5D-3L), and selected items from the Patient-Reported Outcomes version of the Common Term Criteria for Adverse Events (PRO-CTCAE).

Patients will complete the patient-reported outcome measures prior to any assessments at each clinic visit before randomization, prior to the first dose on Day 1 and 22 of every cycle through Cycle 4, and then on Day 1 of all subsequent cycles. In addition, the patient-reported outcome measures will be completed at designated time points during the follow-up period. The primary time points of interest will be Week 12, Week 24, and Week 48.

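### After a hold of both Arm A drugs the scheduled questionnaires wait until dosing restarts, while Arm B's stay on the calendar, and the SAP has no windows or rule for unscheduled forms to align the FKSI-19 comparison

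*Protocol*

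**What the plan says.** Protocol 5.13 (Dosage Modification) sets the visit rules for the two arms in adjacent paragraphs.

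- **Arm A.** "NKTR-214 or nivolumab administration defines a scheduled nominal dosing visit". If a patient is assessed for an intended dosing visit but no drug is given, "any assessments performed during that visit should be recorded as" unscheduled. Then: "When study drug administration resumes, all assessments should be performed as scheduled for the next nominal dosing visit".
- **Arm B.** "Scheduled Cycle X Day 1 and Cycle X Day 22 visits are fixed relative to Cycle 1 Day 1, regardless of dose delays". If dosing is on hold at such a visit, "the cycle visit is not shifted and all assessments should be performed as scheduled".

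The Arm A schedule of events (Protocol 1.2, Table 2) repeats the shift: "If the IV study drug administration is delayed, the procedures scheduled for that visit should be performed with the delayed visit for drug administration". It exempts tumor assessments only. FKSI-19, EQ-5D-3L and PRO-CTCAE are Day 1 and Day 22 procedures in both arms (Tables 2 and 3), so they follow these rules.

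The relevant objective in Protocol 3.2 is "To characterize changes in cancer-related symptoms and quality-of-life in patients with previously untreated advanced RCC" using FKSI-19. Protocol 9.5 plans summary statistics only. SAP 7.6.1 adds a between-arm repeated-measures model (MMRM) for the FKSI-19 total and subscales, with a treatment-by-time term and an assumption of missing at random. SAP 7.6 adds: "The primary time points of interest will be Week 12, Week 24, and Week 48".

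**The concern.** A comparison of symptom scores over time needs both arms measured at comparable times, whatever the patient's condition on that day. Here a stated rule, and not only missing detail, makes the timing depend on the arm. The scheduled Arm A form after a hold is completed once the patient is fit to restart; the Arm B form is completed on its calendar date even if toxicity is ongoing.

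The SAP does not say whether Week 12 means the nominal visit or the calendar week, and it does not say what happens to a form labelled unscheduled. At stake is the interpretation of the FKSI-19 treatment difference at the three named time points.

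**Working it through.** The plan gives no figure for this point, so the check sets the rules side by side and works out the timing.

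**1. Weeks against cycles.** A cycle is 42 days. Day = 7 × week + 1.
- Week 12: day 85. (85 − 1) / 42 = 2 completed cycles, so Cycle 3 Day 1.
- Week 24: day 169. 168 / 42 = 4, so Cycle 5 Day 1.
- Week 48: day 337. 336 / 42 = 8, so Cycle 9 Day 1.

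These matches hold in Arm A only for a patient with no delay.

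**2. Length of the shift.** Protocol 5.13.7 ordinarily allows restart up to 8 weeks after the last dose. The planned interval is 3 weeks. One hold can add 8 − 3 = 5 weeks, so Cycle 3 Day 1 can fall at Week 12 + 5 = Week 17. Medical Monitor agreement can extend this, and repeated holds accumulate. In the same 8 weeks the Arm B calendar has two visits, 3 and 6 weeks on. Through Cycle 4 each carries questionnaires.

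**3. What the form describes.** Restart in Arm A generally requires Grade 1 or baseline (Protocol 5.13.7). FKSI-19 recall is 7 days (Protocol 7.6.1). A form completed at restart therefore mostly describes a recovered or recovering week.

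**4. Whether the SAP corrects it.** There are two readings of Week 12.
- *Nominal visit.* The Arm A record is a later, usually post-recovery score. It is present, so a missing-at-random assumption does not address it.
- *Calendar week.* A held Arm A patient has no scheduled form in that week. Unless an unscheduled form exists and is used, the value is missing because of current toxicity, in Arm A only, and ignorable missingness is doubtful.

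SAP 9.3 states that unscheduled results are included in certain laboratory summaries. SAP 7.6 has no equivalent for questionnaires.

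**5. Illustration of size.** Both inputs are assumed; neither is in the documents. Shift in the Arm A mean = share of patients on hold × score drop during the hold.
- 5% and 4 points: 0.05 × 4 = 0.2. 25% and 8 points: 0.25 × 8 = 2.0.
- With other assumptions, 5% and 2 points: 0.05 × 2 = 0.1. 30% and 6 points: 0.30 × 6 = 1.8.

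Each product treats every hold as symptomatic and of both drugs, with no usable form from the held visit.

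**The case against.** **Forms may exist from held visits.** A reader might infer that Arm A toxicity periods are never captured. The documents do not go that far. Table 2 has patients complete the questionnaire on arrival, before dosing, so someone who attends and is then held may already have done so. The form is kept under the unscheduled label, and no SAP text excludes it. This stands: under-representation is the default effect of the rule, and the use of such forms is undefined.

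**The net direction is open.** A reader might infer a bias in favour of Arm A. But Weeks 12, 24 and 48 all fall on Day 1, and sunitinib is given 4 weeks on and 2 off. A sunitinib patient on schedule is recalling days 36 to 42 of the previous cycle, within the planned off-drug period (days 29 to 42). That works in favour of Arm B. FKSI-19 also covers disease symptoms and function, so a later Arm A form could pick up more disease. This stands.

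**The affected group is limited.** The visit shifts only if neither Arm A drug is given, and 5.13 allows each to be modified separately. Some holds are for laboratory findings: the creditable example is a non-inflammatory creatinine rise, with a delay of about 3 to 5 days, and transaminase rises are described as usually without symptoms (5.13.4). Restart is allowed with Grade 2 fatigue and, in some patients, Grade 2 skin toxicity. This stands, and it is why the figures in step 5 cannot be read as estimates.

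**The stakes are modest.** FKSI-19 is outside the alpha scheme. SAP 7.6 treats EQ-5D-3L and PRO-CTCAE descriptively, and the PRO-CTCAE post-baseline maximum may pick up a held-visit score. This also stands. None of it removes the arm-specific timing rule or the SAP's silence on windows.

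**Conclusion.** The point holds as a difference in measurement rules between the arms that the SAP leaves uncorrected. When both Arm A drugs are held, the scheduled questionnaires move to restart, by up to 5 weeks per hold under the ordinary limit; Arm B's do not move. Taken alone, the hold rule tends to under-represent toxicity periods in Arm A.

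The documents do not establish the net direction or the size of bias in the FKSI-19 comparison. The 0.2 to 2.0 point range is illustrative only, and a clinically material effect should not be inferred from it. The consequence is mainly for the FKSI-19 model. ORR and PFS rest on scans timed from randomization regardless of dose delays, and OS does not depend on these visits. The case for acting is that the correction is cheap.

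**What to change.** 1. **Protocol 5.13 and Table 2.** Exempt FKSI-19, EQ-5D-3L and PRO-CTCAE from the Arm A visit shift, as tumor assessments already are. Collect them at fixed weeks from Cycle 1 Day 1 in both arms, whether or not drug is given. During a hold this can be done at the weekly re-evaluations that 5.13 already asks for, or remotely.
2. **SAP 7.6.** Assign all dated questionnaires, including those labelled unscheduled, to the same calendar windows in both arms, and use those windows as time in the MMRM. State which record counts when two fall in one window. As an example, ±10 days fits visits 21 days apart without overlap (10 + 10 = 20).
3. **SAP 7.6.1.** Add a sensitivity analysis for FKSI-19 records completed during or just after a hold.

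The cost is one sentence in the protocol and table, a windowing rule, one extra analysis, and an occasional questionnaire outside a dosing visit. No dosing rule changes. Both documents need the change: windowing alone cannot recover forms never collected, and would turn a long-delayed visit into a missing value. Neither change removes the sunitinib off-drug week from the Day 1 forms, which should be noted when the results are interpreted.
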